7.1 Inclusion Criteria

A subject must meet all the following criteria to be eligible to participate in this study:

1. Positive for SARS-CoV-2 antigen via nasal swab at or within the past 24 hours of the screening visit detected using an FDA authorized SARS-CoV-2 antigen test.
2. Onset of signs and symptoms consistent with COVID-19* no longer than within the past 3 days* and have either a) a fever of at least 100 °F or b) at least two moderate or severe

symptoms (cough, sore throat, nasal congestion, headache, chills/sweats, muscle or joint pain, fatigue, and nausea) at the time of screening.

3. Provides written informed consent prior to initiation of any study procedures.
4. Be able to understand and agrees to comply with planned study procedures and be available for all study visits.
5. Agrees to the collection of nasopharyngeal swabs, oropharyngeal swabs, oral saliva specimen collection and venous blood specimens per protocol.
6. Agrees to refrain from using oral antiseptics (e.g. hydrogen peroxide rinse, Listerine) or mouthwashes of any kind during the study.
7. Male or non-pregnant female, 18 to 65 years of age, inclusive, at time of enrollment.
8. No uncontrolled disease process (chronic or acute), other than COVID-19 signs and symptoms*.
9. No physical or mental conditions or attributes at the time of screening, which in the opinion of the PI, will prevent full adherence to, and completion of, the protocol.

*The following COVID-19 onset of signs and symptoms generally appear 2-7 days after exposure to SARS-CoV-2:

- Cough
- Sore Throat
- Nasal Congestion
- Headache
- Chills/sweats
- Muscle or joint pain
- Fatigue
- Nausea

Severity of COVID-19 symptoms will be assessed based on definitions used for graded adverse events:

- None (Grade 0): Not present
- Mild (Grade 1): Events that are usually transient and may require only minimal or no treatment or therapeutic intervention and generally do not interfere with the subject's usual activities of daily living.
- Moderate (Grade 2): Events that are usually alleviated with additional specific therapeutic intervention. The event interferes with usual activities of daily living causing discomfort but poses no significant or permanent risk of harm to the research subject.
- Severe (Grade 3): Events interrupt usual activities of daily living, or significantly affects clinical status, or may require intensive therapeutic intervention. Severe events are usually incapacitating.

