9 STUDY ASSESSMENTS AND PROCEDURES

9.1 Screening Assessments

9.1.1 Screening Procedures

At the screening visit, and prior to any other study-related activities, the participating clinical site PI or appropriate sub-investigator will provide the subject with detailed study information and will obtain written informed consent (see section 11.1.1 for more details).

Subject numbers will be assigned with the three-digit numerical site number beginning with numbers greater than one hundred (e.g. 101) followed by an alphanumeric cohort identifier (e.g. C1) and finally a two digit unique numerical identifier assigned with each new subject (e.g. 01).

Example Subject Number: 101-C1-01

COVID-19 Screening

Eligible subjects presenting with uncomplicated COVID-19 must have an oral temperature of at least 100 °F or have at least two moderate or severe symptoms (cough, nasal congestion, or sore throat, headache, chills/sweats, muscle or joint pain, fatigue, or nausea) and consent to be randomized within 3 days of first symptom onset. The subjects will self-assess their COVID-19 symptoms as none (0), mild (1), moderate (2), or severe (3) during screening.

Additionally, subjects who identify with symptomatology associated with COVID-19 will be screened by taking a nasal culture and analyzed for the presence of SARS-CoV-2 by an FDA authorized SARS-CoV-2 antigen test (e.g. BD Veritor™ Plus System, AccessBio Carestart). These systems allow for rapid detection of SARS-CoV-2 via immunoassay for the direct and qualitative detection of SARS-CoV-2 antigens. Subjects presenting at the time of screening that have tested positive via a SARS-CoV-2 rapid antigen test within the past 24 hours and can provide documentation confirming proper identification, the date of the test and testing location, positivity of the result, and name/identity of the assay used to generate the result, are also eligible for enrollment.

There is a small amount of risk to subjects who report mild-to-moderate symptomatology consistent with COVID-19 may have an unknown health problem or co-morbidity at the time of screening that can lead to worsening of condition or hospitalization during study.

General Screening

Some or all of the following assessments are performed during the screening visit to determine eligibility requirements as specified in the inclusion and exclusion criteria:

- Obtain medical history focusing on conditions per protocol exclusion criteria.

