13 APPENDIX 2: TOXICITY GRADING SCALES

Available upon request.

Clarification Memorandum #1 for:
EB-P12-01

A Phase I/II Randomized, Dose Escalation Study to
Evaluate the Safety and Antiviral Activity of the RD-
X19 Device in SARS-CoV-2 Infected Individuals
with Uncomplicated COVID-19

DATE: November 23, 2020

TO: [name]
Senior Clinical Project Manager
SymBio Inc.

FROM: Sponsor's Chief Medical Officer ([name], MD MPH PHD)

SUBJECT: Clarification Memo# 1 to Protocol EB-P12-01, Version
2.0, 11/6/20 entitled, "A Phase I/II Randomized, Dose Escalation
Study to Evaluate the Safety and Antiviral Activity of the RD-X19
Device in SARS-CoV-2 Infected Individuals with Uncomplicated
COVID-19"

This clarification outlines the procedure for documenting emergent signs and symptoms of COVID-19 on Diary Cards vs Adverse Event source documents.

1. Study subjects meeting enrollment criteria related to COVID-19 signs and symptoms are still in a phase of disease pathogenesis where additional COVID-19 signs and symptoms not present at screening may emerge. A timeframe of up to and including study day three will document new COVID-related signs and symptoms as associated with COVID-19 and documented as COVID-19 signs and symptoms with participant-assessed severity scores on diary cards.
2. New signs and symptoms consistent with COVID-19 that first occur on or after study day 4 will be assessed and severity graded and documented as adverse events by site investigators on adverse event source documents. The assessing investigator will be responsible for using their best clinical judgment in assigning attribution of the adverse event.
3. Kindly forward this Clarification Memorandum to Investigators, CRAs and other appropriate staff at the clinical sites. Sites should also forward a copy to their IRBs and maintain a copy with protocol documentation.

Clarification Memorandum #2 for:
EB-P12-01

A Phase I/II Randomized, Dose Escalation Study to Evaluate the Safety
and Antiviral Activity of the RD- X19 Device in SARS-CoV-2 Infected
Individuals with Uncomplicated COVID-19

DATE: December 1, 2020

TO: EB-P12-01 Sites

FROM: Sponsor's Chief Scientific Officer ([name], PHD)

SUBJECT: Clarification Memo# 2 to Protocol EB-P12-01, Version
2.0, 11/6/20 entitled, "A Phase I/II Randomized, Dose Escalation
Study to Evaluate the Safety and Antiviral Activity of the RD-X19
Device in SARS-CoV-2 Infected Individuals with Uncomplicated
COVID-19"

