This clarification outlines the sponsors decision to allow enrollment for up to a 20% overage of the proposed number of subjects.

1. Up to 36 total subjects meeting enrollment criteria related to COVID-19 signs and symptoms may be enrolled per each dose Cohort. This clarification is intended to allow for enrollment of Hispanic subjects for at least 7 days post translation of all study documents into Spanish that was approved and available on November 25th, 2020 for Cohort 1.

STATISTICAL ANALYSIS PLAN

Protocol EB-P12-01

Version 2.0
January 25, 2021

A Phase I/II Randomized, Dose Escalation Study to Evaluate the Safety and Antiviral Activity of the RD-X19 Device in SARS-CoV-2 Infected Individuals with Uncomplicated COVID-19

EmitBio Inc.

[name]
[name]

Approved By:

/s/ [name]	01/25/2021
[name] Director of Statistics Symbio LLC	Date
/s/ [name]	01/25/2021
[name], MPH, PhD Chief Medical Officer EmitBio Inc.	Date
/s/ [name]	01/25/2021
[name] Chief Scientific Officer EmitBio Inc.	Date

CONFIDENTIAL

Table of Contents

1	Purpose of Statistical Analysis Plan	3
2	Study Objectives	3
3	Study Design and Sample Size Determination	3
3.1	Study Design.....	3
3.2	Sample Size Determination.....	4
4	Populations To Be Analyzed	4
5	Planned Analyses	5
5.1	Methodological Considerations	5
5.2	Handling of Missing Data	5
5.2.1	Missing Efficacy Endpoints.....	5
5.2.2	Missing or Incomplete Dates for Adverse Events and Concomitant Medications	5
5.3	Demographics and Baseline Characteristics	6
5.4	Subject Accountability.....	6
5.5	Efficacy Variables and Analyses	6
5.5.1	Analysis of Primary Efficacy Endpoint.....	7
5.5.2	Analysis of Secondary Efficacy Endpoints	7
5.5.3	Analysis of Exploratory Efficacy Endpoint.....	8
5.6	Safety and Tolerability Variables and Analyses	8
5.6.1	Adverse Events.....	8
5.6.2	Vital Signs	9
5.6.3	Methemoglobin	9
5.6.4	Other Assessments	9
6	Tables and Listings	10
7	Appendices.....	10
7.1	Study Schedule of Activities.....	10
7.2	List of Summary Tables, Data Listings and Figures.....	12

Statistical Analysis Plan

1 Purpose of Statistical Analysis Plan

The purpose of the statistical analysis plan is to describe in detail all the data, statistical methods, and summary tables required to implement the statistical analysis of Clinical Study Protocol EB-P12-01 (Section 10 in the study protocol version 2.0 (Amendment 1), dated November 06, 2020).

2 Study Objectives

[figure not shown]

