3.1 Study Design

For the purpose of exploring the above objectives, the study will be conducted as a randomized, double-blind, sham-controlled dose escalation study in SARS-CoV-2 infected individuals with outpatient COVID-19 at two dosing schedules.

This study plans to enroll into two treatment arms within two escalating dose cohorts:

Volunteers meeting all inclusion criteria and none of the exclusion criteria will be randomized to the RD-X19 treatment arm or the sham treatment arm within each cohort in a 2:1 ratio (20 RD-X19 : 10 sham), according to a fixed schedule via a permuted block design and stratified by clinical site. Light will be administered twice daily locally to the mouth and throat only for four days for Cohort 1 and for seven days for Cohort 2.

The clinic visits will occur at:

- Visit 1 / Screening, Enrollment & Randomization

- Visit 2 / Day 2
- Visit 3 / Day 3
- Visit 4 / Day 5 (\pm 1 day)
- Visit 5 / Day 8 (\pm 1 day) / Early Termination (ET)

Assessments of treatment response will occur on study days 3 and 5, with a final determination of efficacy made on day 8 (inclusive).

Efficacy will be evaluated through evaluation of viral load through quantitation of SARS-CoV-2 mRNA by RT-qPCR and via quantitation of replication competent virus by viral titer. Severity of the symptoms of disease will also be aggregated to produce a composite COVID-19 severity score. Safety and tolerability assessments will include solicited and unsolicited adverse events (AEs), physical examinations, vital signs, and clinical laboratory tests.

One unblinded interim analysis is planned upon completion of all subjects in Cohort 1. The results of the interim analysis will be reviewed by a safety monitoring team and a recommendation will be made to the sponsor on whether enrollment should proceed for the next cohort at the next planned dose or at a reduced dosing frequency (e.g. once daily). The study is designed to evaluate at least 2 dosing schedules, ascending, or descending based on safety of each previous cohort.

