5.5.2 Analysis of Secondary Efficacy Endpoints

The following 6 secondary efficacy endpoints will be summarized using descriptive statistics by visit, as appropriate:

- log10-transformed Viral load as measured in saliva by RT-qPCR at each visit by RT-qPCR
- proportion of subjects with $\geq 95\%$ reduction in SARS-CoV-2 viral load by RT-qPCR at each visit
- time to clearance of viral infection in saliva via RT-qPCR
- proportion of subjects demonstrating clearance of viral infection via RT-qPCR at Day 8/ET visit
- COVID-19 composite severity score at each visit
- time to alleviation of COVID-19 symptoms, defined as the number of hours from the first dose to the first time when all eight symptoms had been assessed by the subject as none (0) or mild (1)
- time to sustained alleviation of COVID-19 symptoms, defined the number of hours from the first dose to the time when all eight symptoms had been assessed by the subject as none (0) or mild (1) and no single symptom reoccurs later at a level above mild (1).

Both time to alleviation of COVID-19 symptoms and time to sustained alleviation of COVID-19 symptoms will be derived from self-assessment by study subjects and recorded on the subjects' diary cards.

For log10-transformed viral load data, geometric means will be computed by exponentiating (base 10) the group means of the log10-transformed viral load. Time-to-event variables will be evaluated using the Kaplan-Meier method and p-values for treatment comparison will be provided via log rank test.

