	n (%) Censored	XX (XX.X)	XX (XX.X)	XX (XX.X)
	Median of Time	XX.X	XX.X	XX.X
	25 th , 75 th Percentiles	XX.X, XX.X	XX.X, XX.X	XX.X, XX.X
	95% CI of Median	(XX.X, XX.X)	(XX.X, XX.X)	(XX.X, XX.X)
	P-value RX-X19 vs. Sham	0.XXX	0.XXX	
Per-Protocol	N	XX	XX	XX
	n (%) Censored	XX (XX.X)	XX (XX.X)	XX (XX.X)
	Median of Time	XX.X	XX.X	XX.X
	25 th , 75 th Percentiles	XX.X, XX.X	XX.X, XX.X	XX.X, XX.X
	95% CI of Median	(XX.X, XX.X)	(XX.X, XX.X)	(XX.X, XX.X)
	P-value RX-X19 vs. Sham	0.XXX	0.XXX	

Abbreviation: CI = Confidence Interval

Note 1: Alleviation of COVID-19 symptoms is defined as all eight symptoms assessed by the subject as none (0) or mild (1).

Note 2: Time to alleviation is calculated as the number of hours from the first dose to the time of the first occurrence of symptoms alleviation. Subjects who did not achieve alleviation at the last assessment of study are considered censored at the time of the last assessment.

Note 3: Percentiles and 95% CI of median are derived using the Kaplan-Meier method. P-values for treatment comparison are from Log Rank Test.

Source: Listing 16.2.6.1.2, 16.2.5.3

O:\Studies\EmitBio\EB-P12-01\Biometrics\Programs\Tables\xxx.sas ran on Month Day, Year at hh:mm on data from Month Day, Year.

Figure 15.2.1 - Kaplan-Meier Plot of Time to Alleviation of COVID-19 Symptoms for Intent-to-Treat Population

Figure 15.2.2 - Kaplan-Meier Plot of Time to Alleviation of COVID-19 Symptoms for Per-Protocol Population

Table 14.2.5.2 – Time to Sustained Alleviation of COVID-19 Symptoms

Population	Statistics	4 Days RD-X19	7 Days RD-X19	Sham
Intent-to-Treat	N	XX	XX	XX
	n (%) Censored	XX (XX.X)	XX (XX.X)	XX (XX.X)
	Median of Time	XX.X	XX.X	XX.X
	25 th , 75 th Percentiles	XX.X, XX.X	XX.X, XX.X	XX.X, XX.X
	95% CI of Median	(XX.X, XX.X)	(XX.X, XX.X)	(XX.X, XX.X)
	P-value RX-X19 vs. Sham	0.XXX	0.XXX	
Per-Protocol	N	XX	XX	XX
	n (%) Censored	XX (XX.X)	XX (XX.X)	XX (XX.X)
	Median of Time	XX.X	XX.X	XX.X
	25 th , 75 th Percentiles	XX.X, XX.X	XX.X, XX.X	XX.X, XX.X
	95% CI of Median	(XX.X, XX.X)	(XX.X, XX.X)	(XX.X, XX.X)
	P-value RX-X19 vs. Sham	0.XXX	0.XXX	

Abbreviation: CI = Confidence Interval

Note 1: Sustained alleviation of COVID-19 symptoms is defined as all eight symptoms assessed by the subject as none (0) or mild (1) AND no single symptom reoccurs later at a level above mild (1).

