Listing 16.2.5.3 – Treatment Application Log

Subject	Cohort	Dose Number	Date of Dose	Time of Dose	Missed Dose	Dose Not Applicable	Unknown
Treatment:							

O:\Studies\ EmitBio\EB-P12-01\Biometrics\Programs\Listings\xxx.sas ran on Month Day, Year at hh:mm on data from Month Day, Year

Listing 16.2.6.1.1 – COVID-19 Symptom Assessment and Severity Score

Subject	Cohort	Visit	Assessment		Sore Throat	Nasal Congestion	Headache	Chills/ Sweats	Muscle or Joint pain	Fatigue	Nausea	Fever (F)	COVID-19 Severity Score
			Study Day	Date:Time									
Treatment:													

COVID-19 Symptom: 0=None, 1=Mild, 2=Moderate, 3=Severe. Study Day is calculated relative to date of first treatment. Day 1 is the day of first treatment.

Note: Assessment at a visit was based on symptoms the subject reports as occurring within the past 3 days of that visit.

O:\Studies\ EmitBio\EB-P12-01\Biometrics\Programs\Listings\xxx.sas ran on Month Day, Year at hh:mm on data from Month Day, Year

Listing 16.2.6.1.2- COVID-19 Symptom Assessment and Severity Score from Subject Diary

Site-Subject	Cohort	Not Done	Day	Assessment										COVID-19 Severity Score
				Study Day	Date:Time	Cough	Sore Throat	Nasal Congestion	Headache	Chills/ Sweats	Muscle or Joint pain	Fatigue	Nausea	
Treatment:														
xxxx	x	Day 1- Assessment 1	1											
		Day 1- Assessment 2	1											
		Day 2- Assessment 1	2											

COVID-19 Symptom: 0=None, 1=Mild, 2=Moderate, 3=Severe. Study Day is calculated relative to date of first treatment. Day 1 is the day of first treatment.

Note: Assessment at a visit was based on symptoms the subject reports as occurring within the past 3 days of that visit.

O:\Studies\ EmitBio\EB-P12-01\Biometrics\Programs\Listings\xxx.sas ran on Month Day, Year at hh:mm on data from Month Day, Year

Listing 16.2.6.2 – Clearance of COVID-19 Symptoms

Subject	Cohort	Has there been a timepoint/day that ALL of the subject's Covid-19 symptom assessment scores reached 0 and/or 1?	Date (Study Day)	Time
Treatment:				

Study Day is calculated relative to date of first treatment. Day 1 is the day of first treatment.

O:\Studies\ EmitBio\EB-P12-01\Biometrics\Programs\Listings\xxx.sas ran on Month Day, Year at hh:mm on data from Month Day, Year

Listing 16.2.6.3 – Viral Load via Saliva Specimen and Oropharyngeal Swab Collection

Subject	Cohort	Type of Biospecimen	Visit	Sample Received		Test Date (Study Day)	Test Result	Average N1 Ct	RP Ct	Viral Load Quantitation (copies/mL)

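### Time to first alleviation has no baseline condition, so a subject admitted on fever with no symptom above mild can be counted as alleviated at the first diary entry

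*Combined protocol and SAP*

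**What the plan says.** SAP 5.5.2 lists as a secondary endpoint "time to alleviation of COVID-19 symptoms, defined as the number of hours from the first dose to the first time when all eight symptoms" are none (0) or mild (1), taken from the subject's diary. Table 14.2.5.1 Note 2 repeats the rule: "Time to alleviation is calculated as the number of hours from the first dose to the time of the first occurrence of symptoms alleviation". The note adds censoring at the last assessment for subjects who never reach that state. It says nothing about subjects who are in that state before the first dose.

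Protocol 7.1, item 2, requires recent symptom onset "and have either a) a fever of at least 100" °F or, as the alternative, two or more of the eight symptoms at moderate or severe. The eight are cough, sore throat, nasal congestion, headache, chills/sweats, muscle or joint pain, fatigue and nausea. Fever is not among them; SAP Listings 16.2.6.1.1 and 16.2.6.1.2 give it a separate column.

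The grades needed for a baseline condition are collected. Protocol 9.1.1 states: "The subjects will self-assess their COVID-19 symptoms as none (0), mild (1), moderate (2), or severe (3) during screening". Both symptom listings, however, carry this note: "Assessment at a visit was based on symptoms the subject reports as occurring within the past 3 days of that visit".

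For the parallel viral endpoint the SAP does set a baseline condition: a footnote to Table 14.2.3 removes subjects already cleared at baseline from the time-to-clearance analysis.

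**The concern.** An event called alleviation should mean that something was relieved. For a subject who enters on fever with nothing above mild, and records the same at the first post-dose entry, the event time reflects entry status and the diary schedule, not recovery. The subject may even still be febrile, because the definition does not use temperature.

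These event times would enter the Kaplan-Meier medians, the plots and the log-rank p-values of Table 14.2.5.1, which is also supplied at the Cohort 1 interim. Time to sustained alleviation (Table 14.2.5.2) is affected only for such subjects in whom no symptom later exceeds mild.

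The omission looks unintended. SAP Amendment 1 added the baseline exclusion to Table 14.2.3 and rewrote the definition of time to alleviation, but gave the latter no matching rule and no reason for treating the two differently.

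**Working it through.** The plan gives no power, event count or effect size for this endpoint, so there is no stated figure to reproduce. The check is a trace through the text, followed by illustrations whose inputs are assumptions.

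**1. Trace.**
- Entry: temperature of at least 100 °F with all eight symptoms at 0 or 1 satisfies 2(a).
- Population: ITT (SAP section 4) drops only untreated subjects and those discontinued for baseline CMP/CBC abnormalities. None of the listed major deviations applies, so the per-protocol set does not remove the subject for this reason either.
- Scoring: if the first post-dose diary entry has all eight at 0 or 1, the first-time condition is met and an event is recorded there.
- No rule in the documents blocks this sequence.

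**2. Effect on a median.** Let a share f be scored at the first entry and let the rest have exponential times with true median M. After the first entry the proportion not yet alleviated is (1 − f) × 2^(−t/M). Setting this to 0.5 gives t = M × log2[2(1 − f)]. The result is the same whether affected subjects are placed at 0 h or 12 h, provided the median falls later.

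| Assumed share f | log2[2(1 − f)] | True 72 h reads | True 96 v 48 h reads |
|---|---|---|---|
| 5% | 0.926 | 66.7 h | 88.9 v 44.4 h |
| 10% | 0.848 | 61.1 h | 81.4 v 40.7 h |
| 20% | 0.678 | 48.8 h | 65.1 v 32.5 h |
| 30% | 0.485 | 35.0 h | 46.6 v 23.3 h |

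The true gap of 48 h reads 48 × 0.926 = 44.4 h at 5% and 48 × 0.848 = 40.7 h at 10%. The ratio of medians is unchanged. Nothing in the documents supports the 20% and 30% rows; they show the range only.

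**3. Effect on the log-rank comparison.** Simulation with 20,000 runs per cell (Monte Carlo standard error at most 0.35 points). Assumptions: sham median 96 h, 12-hourly diary, censoring at 168 h, affected subjects given an event at 12 h, same share in both arms. Entries are rejection rates in %, affected subjects kept v excluded.

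| Arms | HR | f = 5% | f = 10% |
|---|---|---|---|
| 20 v 20 | 1.0 | 5.4 v 5.3 | 5.5 v 5.6 |
| 20 v 20 | 2.0 | 45.8 v 47.9 | 42.1 v 45.7 |
| 20 v 20 | 2.5 | 69.3 v 72.1 | 64.6 v 69.5 |
| 20 v 10 | 2.0 | 31.3 v 32.6 | 29.2 v 31.4 |
| 20 v 10 | 2.5 | 50.4 v 52.3 | 47.3 v 50.7 |
| 24 v 12 | 2.0 | 36.6 v 38.6 | 33.6 v 36.2 |
| 24 v 12 | 2.5 | 58.6 v 60.8 | 53.7 v 57.9 |

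The 20 v 20 rows pool sham over cohorts, and the 20 v 10 rows are one cohort. The 24 v 12 rows split 2:1 the enrolment that Clarification Memorandum #2 allows: "Up to 36 total subjects meeting enrollment criteria related to COVID-19 signs and symptoms may be enrolled per each dose Cohort". The largest loss shown is 72.1 − 69.3 = 2.8 points at 5% and 69.5 − 64.6 = 4.9 points at 10%. With no treatment effect, keeping these subjects does not raise the rejection rate; that case was run only at 20 v 20.

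**4. One person.** With the planned 10 sham subjects in Cohort 1, a single such subject drops the sham curve by 1/10 = 10 percentage points at the first entry.

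**The case against.** The strongest reply is about scale. To be affected, a subject must be febrile, have every one of eight symptoms at none or mild, chills/sweats and fatigue included, and still be so at the first post-dose entry. Clarification Memorandum #1 says that "additional COVID-19 signs and symptoms not present at screening may emerge", and it allows for this up to Day 3, which can move subjects out of the group before that entry. If the 3-day look-back governs diary entries, the group narrows further, to those with nothing above mild over those days. The number may be zero. SAP 5.1 calls the p-values descriptive and says the study is not powered for hypothesis testing, and the listings would let an analyst find these subjects afterwards. All of this stands. It limits the size of the problem but does not supply the missing rule.

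It is also fair that SAP 5.5 makes ITT primary, so a restricted set should not replace it. A current-status pre-dose grade may be missing too: the visit note is a look-back, and the diary is handed out on Day 1, when treatment starts. The fix allows for both.

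A reader might infer more than the documents support:
- *All fever entrants score at once.* They do not: one with any symptom above mild at the first entry does not score there.
- *The reported hours cannot be read as symptom relief at all.* That would need a known, material share, and none is given.
- *The interim cohort decision is compromised.* SAP 3.1 describes the dosing schedules as "ascending, or descending based on safety of each previous cohort".
- *Table 14.2.3 is inconsistent because its Day 8/ET row prints no N.* The footnote confines the exclusion to time to clearance, so the ITT rule governs the Day 8/ET row. The printed n (%) lets the denominator be recovered whenever n is above zero.

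**Conclusion.** The gap is real and can be traced in the text without assumptions: a secondary endpoint named for symptom relief counts some subjects who had no qualifying symptom to relieve. Its size is unknown and may be nil. To the extent such subjects are enrolled, medians are shortened and a true difference is diluted. At assumed shares of 5% and 10% a true 72 h median reads about 67 h and 61 h, given exponential times. With equal shares by arm no false effect is created. The consequence is modest, because the endpoint is secondary, its p-values are descriptive and the cohort decision is stated to rest on safety. It still merits correction: in a hypothesis-generating trial the estimated hours are what would be carried forward.

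**What to change.** Follow the approach that Table 14.2.3 already takes for viral clearance, without displacing ITT.

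- **Table 14.2.5.1:** beside the full ITT result, print time to first alleviation restricted to subjects with at least one of the eight symptoms at grade 2 or higher on the pre-dose Day 1 self-assessment. Show the number excluded by arm. State in SAP 5.5.2 that the restricted result is the one to read as time to symptom relief.
- **Table 14.2.5.2:** show the same restricted set beside full ITT. The ITT row still counts entrants who worsen after entry and then recover.
- **Look-back note:** state whether the 3-day note in Listings 16.2.6.1.1 and 16.2.6.1.2 applies to the screening grade and to diary entries. This matters for the flag: under a worst-in-3-days grade, a subject who was moderate two days earlier but mild at dosing would stay in the restricted set and could still score at the first entry.
- **No current-status pre-dose grade:** classify the subject by the recorded screening grade, and report how many were classified this way.

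The cost is SAP wording, one flag and additional table rows, with no new data collection. The downside is a slightly smaller denominator in the restricted rows of a small trial. The flag uses only pre-treatment data, so the restricted comparison remains randomised.
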